Limitation on activity is defined as the inability to fully engage in important life domains, such as cognition, mobility, self-care, and participation in society. For all the hypotheses listed below we will examine change over the 18 month intervention period between the two groups of participants with PTSD: those who are assigned to receive a Service Dog and those who are assigned to receive an Emotional Support Dog.

Hypothesis 1a: Compared to Veterans who receive an Emotional Support Dog, Veterans who receive Service Dogs will have improved ability to fully engage in important life domains over time as measured by the WHO-DAS 2.0 domain scores and the WHO-DAS 2.0 total score.

Hypothesis 1b: Compared to Veterans who receive an Emotional Support Dog, Veterans who receive Service Dogs will have improved quality of life, as measured by the global mental and physical health component scores of the VR-12.

- **Secondary Objectives**

Objective 2: To examine how mental health is impacted by the provision of a Service Dog versus an Emotional Support Dog.

Hypothesis 2a: Compared to Veterans who receive an Emotional Support Dog, Veterans who receive a Service Dog will have reduced PTSD symptom severity, as assessed by the PCL-5

Hypothesis 2b: As compared to Veterans who receive an Emotional Support Dog, Veterans who receive a Service Dog will have decreased thoughts of suicide, as assessed by the Columbia-Suicide Severity Rating Scale (C-SSRS).

Hypothesis 2c: Compared to Veterans who receive an Emotional Support Dog, Veterans who receive a Service Dog will have a decrease in depression as assessed by the PHQ-9.

Hypothesis 2d: Compared to Veterans who receive an Emotional Support Dog, Veterans who receive a Service Dog will have improved sleep outcomes as measured by the Pittsburgh Sleep Quality Index (PSQI)

Objective 3: To characterize and compare how health care utilization and costs are affected by the provision of a Service Dog or Emotional Support Dog.

Hypothesis 3a: Compared to Veterans who receive an Emotional Support Dog, Veterans who receive a Service Dog will have lower health care utilization as quantified by inpatient and outpatient visits to healthcare providers and to mental health providers.

Hypothesis 3b: Compared to Veterans who receive an Emotional Support Dog, Veterans who receive a Service Dog will have decreased medication usage as assessed by the medical record.

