Under the direction of the study economist, the economic statistical analyst will conduct the following activities: The analyst will evaluate economic data submitted on case report forms. Data from initial patients will be evaluated for consistency and interpretability, and feedback provided to study staff via the coordinating center. Periodic reviews of case report forms will continue throughout the study. The research associate will submit continuing review for IRB.

A cohort file, including enrollee social security numbers (SSN’s) from coordinating center, will be obtained. This file will be transmitted securely to the VA Corporate Data Warehouse (CDW). The SSNs of study participants will be used to identify patients in the patient file in CDW, and the associated CDW identifiers for that patient. SSN’s that cannot be found will be flagged for follow-up. Previous trials have demonstrated that transcription errors will be made in about 2-5% of the SSN’s of study enrollees. The economic team will confirm there was VA utilization around time of enrollment. The true social security number will be excluded from subsequent analytical steps. Data on health care cost and utilization of study subjects is extracted from VA administrative files based on the encrypted social security number. The resulting dataset contains the actual date each service was provided.

The analyst will develop and update programs to determine baseline demographics, utilization, and cost, and to determine utilization and cost during trial follow-up period. Cost and utilization data gathered for the economic study can only be accessed by members of the HERC economic study team. Access is restricted to the individuals working on the study: the economist, programmer, and research assistant

3. Activities after study follow-up is complete

The analyst and economist will create a data set of trial participant from case report forms, and VA cost and utilization data. These data will have quarterly observations of health care utilization and cost from study enrollment until the end of follow-up. A repeated measures dataset of employment data will also be created. The economic team will prepare analytic tables and a one or more papers with the economic findings of the trial.

XV. QUALITY CONTROL PROCEDURES

• Standardization/Validation of Measurements

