Secondary continuous variable analyses will include linear repeated mixed model analysis on PTSD Symptom Severity using PCL-5, depression, sleep and thoughts of suicide. Additionally all outcome measures will be examined separately for the observation phase and post-pairing phases of the study. The basis for this analysis is to understand the characteristics of the population in the measures we have selected in their current level of care.

Open-ended questions are asked in the Dog Related Questionnaire. The purpose of these questions is to obtain information about the human-animal bond that occurs for participants that have PTSD and are paired with a SERV or EMOT. The questions will be entered as text based fields into the database. Two assessors will independently review and categorize the data. The assessors will then meet to review their categories. Discrepancies will be discussed with a third assessor to result in consensus of the responses. The categorized responses to these questions will help guide future planning needs, if a program is implemented. Additionally, qualitative measures of symptom status may be developed that are specific to the population of participants that are paired with a Service Dog or Emotional Support Dog. These qualitative measures may be developed as the study progresses by use of focus group or questionnaires.

A complete discussion of the study's statistical monitoring and data analysis is contained in the Statistical Analysis Plan.

- **Economic Outcome Measures**

To characterize and compare how health care utilization and costs are affected by the provision of a Service Dog or Emotional Support Dog, cost and utilization will be assigned to each 3 month period following study enrollment.

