Multivariate regressions will be used to evaluate the effect of assignment to intended treatment and quarter after enrollment to cost and utilization. Generalized Linear Model (GLM) regressions will be used as these avoid the inappropriate assumption of normal distribution and homoscedastic errors (Manning et al., 2001). A Box-Cox regression will be used to identify the appropriate link function (Box & Cox, 1964). A modified Park test will be used to identify the appropriate distributional family. It is likely that these will identify negative binomial regression for the utilization, and a gamma regression to analyze quarterly costs. Standard errors will be corrected for the correlation of multiple observations from the same trial participant over time.

For the employment and work productivity hypotheses, the Work Productivity and Activity Impairment Questionnaire: General Health Problem V2.0 (Reilly et al, 1993). will be utilized. Work productivity will be characterized as Overall Work Productivity (OWP), which is a continuous variable bounded at 0 and 1. OWP is calculated as (Reilly et al, 1993):

$$\text{OWP} = \% \text{ of Work time spent Working} * \% \text{ Productivity at Work}$$

The % of Work time spent Working is calculated as the number of hours worked divided by the sum of the number of hours worked and the number of hours missed work due to health problems. These components are specifically queried by the Work Productivity and Activity Impairment Questionnaire V2.0 (WPAI V2.0).

The WPAI V2.0 queries respondents about their productivity at Work by asking, “During the past seven days, how much did your health problems affect your productivity while you were working?” Respondents answer the question by choosing an integer ranging from 0 to 10. The % Productivity at Work will be calculated as:

$$\% \text{ Productivity at Work} = (\text{Respondent's answer}/10) * 100$$

The WPAI V2.0 also queries respondents about ability to engage in regular daily activities. Respondents are asked, “During the past seven days, how much did your health problems affect your ability to do your regular daily activities, other than work at a job?” Respondents who are not formally employed will have their % Productivity for Activities of Daily Living (ADL) calculated as the following:

$$\% \text{ Productivity for ADL} = (\text{Respondent's answer}/10) * 100$$

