## 2 STUDY OBJECTIVES AND ENDPOINTS

### 2.1 Study Objectives and Hypotheses

#### Primary Objectives:

**Objective 1: To examine how limitations on activity and quality of life in Veterans with PTSD are impacted by the provision of a Service Dog versus an Emotional Support Dog.**

Limitation on activity is defined as the inability to fully engage in important life domains, such as cognition, mobility, self-care, and participation in society. For all the hypotheses listed below we will examine change over the 18-month intervention period between the two groups of participants with PTSD: those who are paired with a Service Dog and those who are paired with an Emotional Support Dog.

*Hypothesis 1a: Compared to Veterans who receive an Emotional Support Dog, Veterans who receive Service Dogs will have improved ability to fully engage in important life domains over time as measured by the WHO-DAS 2.0 domain scores and the WHO-DAS 2.0 total score.*

*Hypothesis 1b: Compared to Veterans who receive an Emotional Support Dog, Veterans who receive Service Dogs will have improved quality of life, as measured by the global mental and physical health component scores of the VR-12.*

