### 3.7 Follow-up

The primary objective of this study is to determine how the provision of a Service Dog or an Emotional Support Dog impacts function and quality of life for Veterans with PTSD. Primarily, the objective is to compare functioning and quality of life change, relative to baseline, over the 18-month intervention period between the two groups of Veterans with PTSD, i.e., those who receive Service Dogs and those who receive Emotional Support Dogs. The secondary outcomes in this study are: 1) a reduction in PTSD symptoms as measured by the PTSD Civilian Checklist (PCL); 2) improvement in depression as measured by the PHQ-9; 3) improvement in sleep as measured by the Pittsburg Sleep Quality Index (PSQI); 4) decreased thoughts of suicide as measured by the Columbia-Suicide Severity Rating Scale (C-SSRS); and 5) to characterize and compare how healthcare costs and utilization are impacted. All primary and secondary outcome measures will be collected at baseline, clearing, and at 3, 6, 9, 12, 15 and 18 month post-pairing. The following forms will be used during the follow-up phase of the study.

Table 2. Follow-up Phase Data Forms

Form #	FORM Name	1 week	2 week	1 month	2 month	3 month	6 month	9 month	12 month	15 month	18 month
	PHASE	2	2	3	3	3	3	3	3	3	3
	VISIT #	01	02	01	02	03	06	09	12	15	18
	LOCATION	Home	H/P	Home	H/P	Clinic	Home	Clinic	Home	Clinic	Home
3	CAPS										R
7	WHO-DAS 2.0					R	R	R	R	R	R
8	PCL-5					R	R	R	R	R	R
9	PSQI					R	R	R	R	R	R
10	VR-12					R	R	R	R	R	R
11	C-SSRS					R	R	R	R	R	R
12	PHQ-9					R	R	R	R	R	R
13	DAR					R	R	R	R	R	R
14	HERC Non-VA Utilization					R	R	R	R	R	R
15	WPAI: GHP v2.0					R	R	R	R	R	R
17	Medication Log	A	A	A	A	A	A	A	A	A	R
18	Payment Log	A	A	A	A	A	A	A	A	A	R
19	Post Pairing Evaluation	R	A	A	A	A	A	A	A	A	A
20	Veteran and Service/ES Dog Visit Report	R	A	R	A	A	R	A	R	A	R
21	Dog Related Questions	R	R	R	R	R	R	R	R	R	R
22	Dog Return	A	A	A	A	A	A	A	A	A	A
23	Veterinarian Checklist	R					R		R		R
24	Study Completion/Termination	A	A	A	A	A	A	A	A	A	R
24a/b	Exit Interview – SERV or Exit Interview – EMOT										R
24c	Dog Trainer Evaluation										R
25	Protocol Deviation	A	A	A	A	A	A	A	A	A	A
26	Adverse Events	A	A	A	A	A	A	A	A	A	A
26a	Adverse Events for Dogs	A	A	A	A	A	A	A	A	A	A
27	Serious Adverse Events	A	A	A	A	A	A	A	A	A	A
27a	Serious Adverse Events for Dogs	A	A	A	A	A	A	A	A	A	A
28	AE/SAE Follow-up	A	A	A	A	A	A	A	A	A	A
28a	SAE Follow-up for Dogs	A	A	A	A	A	A	A	A	A	A

H/P = HOME/PHONE

R = REQUIRED

A = AS NEEDED

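### Cost and utilization are counted from enrollment, so the arm effect for Hypotheses 3a-3c, fitted with the terms named, includes at least one quarter without a dog

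*Protocol*

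**What the plan says.** **The clock.** Protocol XVIII, Economic Outcome Measures, states that "cost and utilization will be assigned to each 3 month period following study enrollment". Protocol XIV (activities after follow-up is complete) builds a dataset with "quarterly observations of health care utilization and cost from study enrollment until the end of follow-up".

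**The model.** The same part of Protocol XVIII describes multivariate regressions for "the effect of assignment to intended treatment and quarter after enrollment to cost and utilization". No phase term, pairing date, interaction or baseline covariate is named. SAP 7.2.2 refers the reader back to the protocol. Protocol XIV does plan programs "to determine baseline demographics, utilization, and cost, and to determine utilization and cost during trial follow-up period", but the baseline values are not carried into the model description.

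**The wait.** The observation phase lasts at least three months (Protocol VII; SAP 3.5 counts it from randomization). At least three months separate vendor interview and pairing (Protocol VIII). Protocol XVIII sets no upper limit, and Protocol II expects waits of more than three months. Participant and site do not learn the dog type until the Home Clearing visit (Protocol VIII; SAP 3.4).

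**The window promised elsewhere.** SAP 3.1 follows participants for 18 months after pairing to determine primary and secondary outcomes, and SAP 2.2.2 lists utilization and cost as secondary. Protocol III says: "For all the hypotheses listed below we will examine change over the 18 month intervention period". SAP 2.1 repeats that "we will examine change over the 18-month intervention period between the two groups". SAP 3.7 lists cost and utilization among the secondary outcomes and adds: "All primary and secondary outcome measures will be collected at baseline, clearing, and at 3, 6, 9, 12, 15 and 18 month post-pairing".

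**The concern.** Hypotheses 3a-3c ask whether receiving a Service Dog rather than an Emotional Support Dog lowers utilization and medication use. In the waiting period nobody has a dog, and neither participant nor site knows the arm, so no arm difference is expected there. A single arm coefficient fitted over all quarters since enrollment averages those empty quarters with the quarters that carry the effect. How far it shrinks depends on dog supply rather than on the dogs.

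The results are meant to inform benefits policy (Protocol I). A modest true difference in cost or utilization would be more likely to be reported as null, and the result would not describe the post-pairing window that SAP 3.1 sets.

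**Working it through.** **1. The plan's own figure.** No sample size or power is given for Hypotheses 3a-3c. The trial's size rests on the MCS: difference 0.15 x 33.2 = 4.98, SD 10.6, two-sided alpha 0.05, power 0.85. Then n = 2 x (1.960 + 1.036)^2 x 10.6^2 / 4.98^2 = 81.4, so 82 per group, and 82 / 0.75 = 109.3, so 110 per arm. Both reproduce.

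**2. Dog-free share.** Enrollment is not tied to one event. Consent, baseline, randomization and entry to the observation phase all fall at least three months before the dog. Let w be the dog-free quarters; six post-pairing quarters follow. With equal weights, a constant post-pairing effect and no arm effect before pairing, the common arm effect keeps 6/(6 + w) of the post-pairing effect.

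| Wait | w | Dog-free share | Effect kept | Assumed ratio 0.80 becomes (log scale) |
|---|---|---|---|---|
| 3 months (documented minimum) | 1 | 1/7 = 14% | 0.86 | 0.80^(6/7) = 0.826 |
| 6 months (assumed) | 2 | 2/8 = 25% | 0.75 | 0.80^0.75 = 0.846 |
| 9 months (assumed) | 3 | 3/9 = 33% | 0.67 | 0.80^0.667 = 0.862 |

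Nine months would arise if a participant were given a new vendor six months after interview and the three-month minimum then ran again (6 + 3), with the enrollment clock not restarted. Protocol VIII says only that this may happen. Averaging means rather than logs, as a count model does, gives 0.829, 0.850 and 0.867.

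**3. Sample-size cost of the clock alone.** Take an exchangeable within-person correlation rho (assumed). The variance of a mean of m quarters is v(m) = (1 + (m - 1) rho)/m. The required sample for the listed model, relative to an unadjusted post-pairing model, is [v(7)/(6/7)^2] / v(6) at w = 1:

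- rho 0.3: (0.400/0.735)/0.417 = 1.31
- rho 0.5: (0.571/0.735)/0.583 = 1.33
- rho 0.7: (0.743/0.735)/0.750 = 1.35

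**4. What baseline adjustment adds.** Adjusting the post-pairing mean for one earlier quarter gives variance v(6) - rho^2. Relative to the unadjusted post-pairing model the saving is 0.417/0.327 = 1.28, 0.583/0.333 = 1.75 and 0.750/0.260 = 2.88 for rho 0.3, 0.5 and 0.7. This gain is separate from the clock.

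**5. Power illustration.** Take a contrast with 85% power on six post-pairing quarters at 82 per arm, and rho from 0.2 to 0.8. Power falls to about 73-75% with one dog-free quarter and 62-66% with two.

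**6. Employment and productivity.** Protocol XVIII uses the same clock for Hypotheses 4a-4b. The WPAI has a seven-day recall at visits, so after Baseline 1 there are seven records (Baseline 2 and months 3, 6, 9, 12, 15, 18) and one of the seven is dog-free. Hypothesis 4a is already worded for follow-up, and Protocol XIV separates baseline from follow-up visits.

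**The case against.** **Counting from enrollment by assigned arm is a legitimate intention-to-treat cost analysis.** This stands, and that analysis should be kept. What is missing is a statement that it is the intended contrast, reconciled with SAP 3.1.

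**The protocol gives prose, not an equation.** This also stands. Multivariate regression does not exclude other terms, and baseline cost and utilization are to be derived, so the dilution follows only if the model is fitted with the terms named. An arm-by-quarter interaction would not cure it, because waits vary and enrollment quarters do not line up with pairing.

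**The plan has other views.** Protocol XVIII will examine all outcomes separately for the observation and post-pairing phases, and will use both randomized and paired populations. It would be wrong to infer that no post-pairing look exists. But the phase look is justified as describing the population in its current care, and the choice of population does not move the clock. Neither is named as the test of Hypotheses 3a-3c.

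**The 18-month wording does not clearly reach cost.** This stands in part. A reader might take the 18-month sentence in SAP 3.7 as covering cost; it names only functioning and quality of life. The sentences in Protocol III and SAP 2.1 sit under Objective 1, although they speak of all hypotheses listed below. The SAP 3.7 visit schedule includes baseline and clearing. These support the point; SAP 3.1 carries it.

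**The outcomes are secondary and the distortion is conservative.** This is true while waits are balanced by arm, which no section guarantees.

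**Conclusion.** The point holds as a mismatch between the economic clock and the post-pairing window, and it should be corrected. At the documented minimum wait the common arm effect keeps at most 6/7 (0.86) of a constant post-pairing effect, and the clock alone costs about a 1.3-fold larger sample. Longer waits make it worse: 0.75 at an assumed 6 months, 0.67 at an assumed 9. The size rests on fitting only the listed terms, equal quarter weights, an immediate and constant effect, and an assumed within-person correlation.

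Two stronger readings are not supported:

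- A reader might multiply steps 3 and 4 of the working and charge the clock with a 1.7- to 3.9-fold loss. The part beyond about 1.3 comes from the absent baseline covariate, which is a separate improvement.
- A reader might infer inflated false positives. With balanced waits the pull is toward no difference. Waits that differed by arm could distort the contrast in either direction, but the documents give no evidence that they will differ.

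For Hypotheses 4a-4b the issue is smaller.

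**What to change.** In Protocol XIV and XVIII:

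- Define enrollment.
- Name as the test of Hypotheses 3a-3c the comparison by assigned arm over the 18-month intervention period, with quarters indexed from the Home Clearing (unblinding) date. This keeps participants lost between unblinding and pairing. That matters because not accepting the assigned dog type is a listed termination reason (Protocol XII).
- Adjust for cost and utilization measured before that date, while participant and site are still blinded.
- Report the enrollment-clock analysis of all randomized participants alongside, labelled intention to treat.
- Use a clock from the pairing date only as a sensitivity analysis. First reconcile the Service Dog pairing date: departure from training in Protocol X, the day training begins in SAP 6.4. Its baseline covariates must still stop at unblinding. The time between unblinding and pairing differs by arm: 1-2 weeks at the vendor against 1-2 days at home (Protocol IX).
- For Hypotheses 4a-4b, use the month 3-18 WPAI records as outcomes and the Baseline 1 and Baseline 2 values as covariates.

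**Cost.** Wording and modest programming: Protocol XIV already extracts service dates and derives baseline cost and utilization. There is one more estimate to report. Participants lost before Home Clearing appear only in the intention-to-treat estimate. A short dog-free interval between Home Clearing and pairing remains in the main estimate.

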Hypothesis 3c: Compared to Veterans who receive an Emotional Support Dog, Veterans who receive a Service Dog will have decreased use of sleep medications as assessed by the medical record.

Objective 4: To characterize and compare how employment and productivity are affected by the provision of a Service Dog or Emotional Support Dog.

Hypothesis 4a: Compared to Veterans who receive an Emotional Support Dog, Veterans who receive a Service Dog will be more likely to be employed at follow-up.

Hypothesis 4b: Compared to Veterans who receive an Emotional Support Dog, Veterans who receive a Service Dog will have greater work productivity as quantified by the Work Productivity and Activity Impairment Questionnaire: General Health Problem V2.0.

IV. STUDY OUTCOME MEASURES

Primary Outcomes: The primary outcome measures are limitations of activities and quality of life.

Hypothesis 1a: The total score and six domain scores as measured by the World Health Organization Disability Assessment Scale II (WHO-DAS 2.0) will define activity limitations. The WHO-DAS 2.0 is a structured 36-item instrument, which assesses difficulties in six domains of life during the last 30 days. The domains include:

1. Cognition: understanding and communicating with the world
2. Mobility: moving and getting around
3. Self-care: attending to one's hygiene, dressing, eating and staying alone
4. Interpersonal interactions: getting along with people
5. Life activities: domestic responsibilities, leisure, and work
6. Participation in society: joining in community activities

Hypothesis 1b: The outcome measure will be the summary measures from the VR-12 instrument of health related quality of life as measured by both the Physical Component Summary (PCS) and Mental Component Summary (MCS) scores.

Secondary Outcomes: Secondary outcomes include PTSD severity and symptoms, depression, sleep, suicide intent, healthcare utilization, healthcare cost, and employment.

Hypothesis 2a: The outcome measure will be the Posttraumatic Stress Disorder Checklist (PCL-5). The PCL-5 is a 20-item self-report measure of PTSD symptoms (in the past month) based on DSM-5 criteria with a 5-point Likert scale response format.

Hypothesis 2b will examine suicidal ideation, which will be assessed by the Columbia-Suicide Severity Rating Scale (C-SSRS).

Hypothesis 2c examines depression, which will be assessed by the Patient Health Questionnaire (PHQ-9).

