Participants will be queried regarding their non-VA utilization using the HERC-developed standard questions regarding outpatient and inpatient utilization (including Emergency Department visits). The mean VA DSS unit cost will be used for the same type of utilization for the cohort of PTSD patients as estimates of the cost of these non-VA services.

Participants will be asked for an authorization under HIPAA for use of VA data on the quantity and cost of health services they use during the trial. Participants will be queried regarding their employment and work productivity at baseline and during each follow-up visit, using the Work Productivity and Activity Impairment Questionnaire: General Health Problem V2.0 (Reilly et al, 1993). The questions in this survey will be rephrased to ask about the effect of PTSD on employment and productivity. The WPAI V2.0 queries respondents about their productivity at Work by asking, "During the past seven days, how much did your health problems affect your

productivity while you were working?” Respondents answer the question by choosing an integer ranging from 0 to 10. The WPAI V2.0 also queries respondents about ability to engage in regular daily activities. Respondents are asked, “During the past seven days, how much did your health problems affect your ability to do your regular daily activities, other than work at a job?”

- **Activities of Economic Team**

The economic team will be responsible for data evaluation and analysis in different phases of the study, as described below.

1. Activities prior to start-up

The economic team will create study forms pertaining to economic data. The team will review the HIPAA waiver and research consent forms to be sure that they include economic data and describe the participation of the economic team. An application to use cost and utilization data, and to work with the social security numbers of study participants, will be submitted to National Data Systems. A “study binder” will be created with regulatory documents, protocol, and other documents.

2. Activities after study enrollment begins

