Multivariate regressions will be used to evaluate the effect of assignment to intended treatment and quarter after enrollment on employment and on overall work productivity. Generalized Linear Model (GLM) regressions will be used, with Box-Cox regression used to identify the appropriate link function. A modified Park test will be used to identify the appropriate distributional family. Standard errors will be corrected for the correlation of multiple observations from the same trial participant over time. Two sets of analyses will be run for productivity. The first set of analyses will focus on work productivity and assign a value of 0% productivity to any individual who is not employed. The second set of analyses will focus on overall productivity and will use % Productivity at Work as a data point if the respondent was formally employed and % Productivity for ADL as a data point if the respondent was not formally employed.

- **Missing Data**

For this study we will collect data by in-person interviews and home visits, therefore we expect minimal missing data. When missing data are encountered in the analyses, a detailed sensitivity analysis can be conducted of the effects of various assumptions about the missing data. When needed, missing data will be imputed using standard multiple imputation techniques.

- **Interim Monitoring**

An independent oversight committee, a Data Monitoring Committee (DMC) will be monitoring study progress at predetermined time points over the entire duration of the study. The committee will receive analyses of the primary and the secondary outcome measures on a routine basis. Additionally, the committee will receive data on the participants enrolled, description of the reasons for participant exclusion, adverse events and each centers performance with regard to participant intake and follow-up. In general, this committee meets at six to nine months after the start of participant recruitment and at least annually (sometimes semiannually) thereafter. The committee will receive reports about three weeks prior to the meetings. Since the primary outcome measures are at 18 months, sufficient data for DMC's first review will not be available until the study has been ongoing for at least two years.

- **Criteria for Study Termination**

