#### **2.3.9 Employment/Productivity**

Veteran’s employment status and work productivity will be assessed through the Work Productivity and Activity Impairment Questionnaire: General Health Problem V2.0 (WPAI:SHP). The WPAI is the most frequently-used instrument to assess work productivity (Prasad et al., 2004). The WPAI: GHP is a 6-item questionnaire that can be interviewer-administered or completed by a respondent (Reilly et al., 1993). The questionnaire asks about the number of hours of work missed due to health problems as well as the effect of the health problems on productivity while at work.

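### Both WPAI productivity formulas score impairment as productivity: the overall-productivity comparison changes sign and the OWP measure for Hypothesis 4b is distorted

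*Protocol*

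**What the plan says.** Hypothesis 4b (Protocol III; repeated in SAP 2.1) predicts that Veterans given a Service Dog "will have greater work productivity as quantified by the Work Productivity and Activity Impairment Questionnaire".

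Protocol XVIII, Economic Outcome Measures, gives the scoring:

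- The work item asks "how much did your health problems affect your productivity while you were working". The text continues "Respondents answer the question by choosing an integer ranging from 0 to 10. The % Productivity at Work will be calculated as", and the formula that follows is (answer/10) x 100.
- The daily-activities item asks how far health problems affected regular activities outside a job. For respondents without formal employment, % Productivity for ADL is again (answer/10) x 100.
- OWP is the share of work time actually worked, i.e. hours worked/(hours worked + hours missed for health), multiplied by % Productivity at Work. It is said to lie between 0 and 1.

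Two analyses follow. The first, on work productivity, will "assign a value of 0% productivity to any individual who is not employed". The second, on overall productivity, "will use % Productivity at Work as a data point if the respondent was formally employed" and takes % Productivity for ADL otherwise.

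Protocol XIV adds: "The questions in this survey will be rephrased to ask about the effect of PTSD on employment and productivity". SAP 2.3.9 describes the questionnaire as covering hours missed "as well as the effect of the health problems on productivity while at work" but gives no scoring rule. SAP 7.2.3 gives none either and refers back to the protocol.

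**The concern.** A larger answer to a question about how much health problems affected productivity means more impairment. The printed formulas turn that answer directly into a score called productivity, so a respondent reporting no effect (0) scores 0% productive and one reporting the greatest effect (10) scores 100%.

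The surrounding rules show that a high score was meant to be good. The work-time factor in OWP rises with productivity, and the first analysis gives people without a job 0%. As printed, a full-time worker with no impairment also gets an OWP of 0, the same as someone with no job.

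These formulas are the only prespecified scoring for Hypothesis 4b. Followed literally, the second analysis would report a true benefit of Service Dogs as harm and a true harm as benefit. OWP would mix a correctly oriented quantity with an inverted one.

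**Working it through.** **Inputs.** The item wording, the 0-10 range, the formulas and the two analysis rules come from Protocol XVIII. The protocol prints no productivity result to reproduce. Mean answers, employment rates and work-time shares below are illustrations, because the documents give none. Direction assumption: 0 = no effect, 10 = greatest effect.

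**Score for one respondent.** Printed: P = (answer/10) x 100. Intended: (1 - answer/10) x 100 = 100 - P.

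| Answer | Printed | Intended |
|---|---|---|
| 0 | 0% | 100% |
| 2 | 20% | 80% |
| 5 | 50% | 50% |
| 8 | 80% | 20% |
| 10 | 100% | 0% |

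**Second analysis.** Every data point is either the work score or the ADL score, so every data point is 100 minus the intended value. The difference in raw means therefore changes sign and keeps its size, whatever the employment mix.

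- Mean answers 3 (SERV) and 5 (EMOT): printed 30 - 50 = -20; corrected 70 - 50 = +20.
- Employment 70% and 40%, work answers 3 and 5, ADL answers 4 and 6. Printed SERV: 0.7 x 30 + 0.3 x 40 = 33. Printed EMOT: 0.4 x 50 + 0.6 x 60 = 56. Difference -23. Corrected: 67 - 44 = +23.

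**OWP.** Let E be the share employed, T the fraction of work time worked and a the mean work answer, with non-employed participants at 0 and percentages read as proportions. If T and a are uncorrelated among the employed, mean OWP is E x T x a/10 as printed and E x T x (1 - a/10) corrected. SERV minus EMOT:

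| E (SERV/EMOT) | T (SERV/EMOT) | a (SERV/EMOT) | Printed | Corrected |
|---|---|---|---|---|
| .40/.40 | .95/.95 | 3/5 | .114 - .190 = -.076 | .266 - .190 = +.076 |
| .45/.40 | .95/.95 | 3/5 | .128 - .190 = -.062 | .299 - .190 = +.109 |
| .70/.40 | .95/.95 | 4/5 | .266 - .190 = +.076 | .399 - .190 = +.209 |
| .50/.40 | .95/.95 | 7/7 | .3325 - .2660 = +.0665 | .1425 - .1140 = +.0285 |
| .40/.40 | .95/.85 | 3/3 | .114 - .102 = +.012 | .266 - .238 = +.028 |
| .40/.40 | .95/.85 | 5/5 | .190 - .170 = +.020 | .190 - .170 = +.020 |

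The first two rows are reversed, the third and fifth are too small, and the fourth is about 2.3 times too large (.0665/.0285). The last is unchanged only because a mean answer of 5 scores 50% either way.

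**When the printed OWP sign is wrong.** The printed difference is zero when E x T x a is equal in the two arms. Suppose SERV has the lower mean answer and no less employment or work time. The printed sign is then wrong unless the SERV/EMOT ratio of E x T exceeds the EMOT/SERV ratio of mean answers: 5/4 = 1.25 for answers 4 and 5, and 5/3 = 1.67 for answers 3 and 5. Check at 1.25 (E .50/.40, T .95, answers 4/5): printed .190 - .190 = 0; corrected .285 - .190 = +.095.

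**The case against.** The strongest objection is that the direction is inferred. Neither document prints the 0 and 10 labels, the form itself is not reproduced, and the items are to be rephrased for PTSD. The SAP is also inconsistent about the instrument's name, using SHP in places where the protocol has GHP. If the labels ran against the question, the printed formulas would be right. This stands as a stated assumption. However, the rephrased items would still ask about an effect, and the work-time factor and the 0% for the non-employed make sense only if a high score means more productive.

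Second, Hypothesis 4b concerns work productivity, which the protocol measures with OWP, whereas the full reversal belongs to the analysis described as overall productivity. That is a fair limit: OWP is distorted, and its sign need not change.

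Third, the exact mirror image holds for raw means only. The plan is a GLM with a link chosen by Box-Cox regression. Under a log link, the 3 versus 5 example gives a mean ratio of 30/50 = 0.60 printed and 70/50 = 1.40 corrected. The direction flips, but the ratios are not reciprocals (1/0.60 = 1.67).

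Fourth, the OWP figures and the 1.25 and 1.67 thresholds assume that impairment and hours missed are uncorrelated among workers, which may fail. The second-analysis result does not need this.

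Finally, the economics centre may score the items correctly in practice. That would be an undocumented departure from the only written rule.

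**Conclusion.** The concern holds: both formulas are wrong as written, given that 10 denotes the greatest effect. In the second productivity analysis the raw mean difference has the right size and the wrong sign. In OWP one of two factors is inverted, so the group difference may be reversed, attenuated, inflated or unchanged, depending on employment, hours missed and the level of the answers. It cannot be read as productivity. The numerical sizes are illustrations; the sign change in the second analysis follows from the formulas alone. The damage is confined to a secondary hypothesis: the primary outcomes, the sample size of 220 and Hypothesis 4a on employment status do not depend on these scores. It should be fixed before analysis.

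**What to change.** 1. Confirm the 0 and 10 labels and the final item wording on the WPAI form (form 15), and print both in the SAP.
2. If 10 is the greatest effect, define % Productivity at Work and % Productivity for ADL each as (1 - answer/10) x 100.
3. Define OWP = [hours worked/(hours worked + hours missed)] x (1 - answer/10), which also settles the 0-1 scale that the printed factor of 100 leaves unclear.
4. Put this rule in SAP 7.2.3 before the analysis, correct the protocol formulas to match, and use one name for the instrument throughout.

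The cost is two formula corrections and one SAP paragraph. The raw 0-10 answers and hours are already collected, so no new data are needed.
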